4.2.3 Impact of COVID-19 pandemic on study data

Missing data is expected to be one of the major implications of the COVID-19 pandemic. The following approaches/strategies will be applied to assess the impact of COVID-19 pandemic on study data.

- Added an eCRF page “COVID-19 Impact”, including impacted visits, impact categories and relationship to COVID-19;
- Additional fields were added in protocol deviation specification documents to record protocol deviations relationship to COVID-19 pandemic;
- Included additional summary analyses based on the timing of COVID-19 impact (pre/during/post COVID-19 pandemic).

4.3 Handling of repeated and unscheduled measurements

All repeated and unscheduled measurements will be presented in the listings, where applicable. The following general rules will apply to all repeated and unscheduled measurements:

- For repeated or unscheduled measurements obtained prior to the first dose of IMP the latest non-missing value (scheduled or unscheduled) will be used in the calculation of descriptive statistics (e.g. repeated measurements during the Screening period);
- For repeated or unscheduled measurements obtained at any time point after the first dose of IMP, the scheduled values (if non-missing) will always be used in the calculation of changes from Baseline and for the descriptive statistics (ie, in summaries by time point). If repeated scheduled values are obtained at any time point, the latest non-missing values will be used.

See [Sections 8.4.2](#) for the rules applied to ECG triplicate measurements.

4.4 Interim analyses and data monitoring

There is no interim analysis planned for this study.

An independent Data Monitoring Committee (IDMC) will oversee the safety of the study by reviewing safety data at periodic data reviews.

The safety data of this study will also be pooled with other Rozanolixizumab studies and reviewed by the overarching DMC. The details of overarching DMC will be described in a separate document.

4.4.1 Timing for periodic data reviews

The safety data review (SDR) meetings will be held in collaboration with the MG0003 study team. The orientation SDR meeting of this study will be held at the first SDR meeting of MG0003 study.

First SDR meeting will be initiated when approximately 10 study patients have been randomized over 26 weeks and held at the second SDR meeting of MG0003 study. Ad-hoc meeting will be held based on the agreement of the IDMC.

4.4.2 Data required for periodic data reviews

All available data at the time of the data cut-off will be included at each SDR. The database will not be locked, but the data should be as clean as possible, and it is not required to have resolved all queries prior to each database snapshot. Study enrollment will not be halted during planned IDMC review of the safety and efficacy data.

Required safety data to be used to support the SDR will include the following:

- Adverse events
- ECGs
- Vital signs
- Medical and procedure history
- Prior and concomitant medications
- Demographics
- Safety labs (hematology, chemistry, urinalysis)
- Total IgG
- Pregnancy
- Columbia-Suicide Severity Rating Scale (C-SSRS)

These data will be summarized using descriptive statistics. Data will also be provided in listings.

4.5 Multicenter studies

Individual center results will not be displayed.

4.6 Multiple comparisons/multiplicity

Adjustment for multiplicity will not be required since all analyses will be descriptive in nature.

4.7 Use of an efficacy subset of study participants

Efficacy data will be summarized only, and there is no sensitivity analysis planned.

4.8 Active-control studies intended to show equivalence

Not applicable.

4.9 Examination of subgroups

The continuous secondary efficacy endpoints will be evaluated for subgroups of interest including:

- Age (18 to <65 years, ≥65 years)
- Age (18-<65, 65-<85, ≥85 years)
- Sex (male, female)
- Region (North America, Europe, and Asia [excluding Japan], Japan)
- Stratification factor in MG0003 - MG-specific autoantibody (MuSK+ or AChR+)

Notes: Region captured from MG0003 CRF will be used. The stratification factors MuSK(+/-) and AChR(+/-) will be based on the derived values from MG0003 subgroup analysis.

The MG-ADL scores and change from Baseline will be summarized in the five subgroups as above and additional subgroups as follow:

- Duration of disease at Baseline (<median, ≥ median)
- MGFA disease class at Baseline
- Thymectomy at Baseline (yes, no)
- Baseline MG-ADL category (<5, ≥5).

These evaluations will be descriptive; no statistical testing of treatment-by-subgroup interactions nor statistical testing of treatment effects within subgroups will be carried out.

Subgroup analyses will only be performed for cases where there are at least 5 participants in a particular category, otherwise it will not be performed.

5 STUDY POPULATION CHARACTERISTICS

5.1 Subject disposition

The following outputs will be created.

Summaries:

- **Reasons for screen failures** (as collected on the Study Termination Screen Failure CRF page) will be summarized using the ES for overall. Additionally, the reasons for screen failures will be summarized by pre-, during and post- the COVID-19 pandemic based on the screen failure date relative to the pandemic cut-off date.
- **Disposition of study participants screened** will be summarized using the ES for overall, by region and by site. In this summary, the site number, principal investigator name, first participant in date and last participant out date, will be captured by randomized treatment and by each analysis set (RS and SS).
- **Disposition of analysis sets** will be summarized by treatment groups and analysis sets (RS and SS) using the RS.

- **Disposition and discontinuation reasons** using the RS and SS will contain the number and percentage of study participants by treatment group and RLZ total and also by pre-, during and post- the COVID-19 pandemic who:
 - Started Study,
 - Completed Study,
 - Discontinued Study with
 - Primary Reason for discontinuation, including transitioned to study MG0007 (primary reason for premature study termination as collected in the Study Termination Enrolled CRF).

Note: The summary by pre-, during and post- the COVID-19 pandemic will be based on the start, completed and discontinuation date relative to the pandemic cut-off date will be presented in the same table. The discontinuation reason in each period will also be summarized. Discontinuation due to COVID-19 pandemic will be listed as sub-category under “Other” reason.

- **Discontinuation due to AEs** using the RS and SS will summarize the total number of study participants who discontinued the study due to AEs by treatment group and the categories: AE, serious fatal, AE non-fatal and other (AE non-serious fatal).
- **Count of participant by visit** using SS will summarize the number of participants at each visit by treatment group.
- **Impact of COVID-19 pandemic** using the RS will summarize number and percentage of participants in each impact category by visit.

Listings of study participant disposition, study discontinuation and study participants who did not meet study eligibility criteria will be provided.

5.2 Important Protocol deviations

A summary of number and percentage of participants with an important protocol deviation by relationship to COVID-19 pandemic and treatment group will be provided for the RS. Additionally, the summary will be repeated by pre-, during and post- the COVID-19 pandemic based on the deviations start date relative to the pandemic cut-off date.

A listing of important protocol deviations will be provided based on the RS.

6 DEMOGRAPHICS AND OTHER BASELINE CHARACTERISTICS

6.1 Demographics

Demographic variables will be summarized on the RS and SS, by categories mentioned below using descriptive statistics by treatment group and RLZ total. Additional subgroup summary will be presented by pre-, during and post- the COVID-19 pandemic based on the enrolled date relative to the pandemic cut-off date.

Categories for continuous variables (including n, mean, SD, Median, Min and Max):

- Age at the time of Study MG0003 entry (years)

Notes: Missing age will be calculated as year of informed consent signed – year of birth

- Height (cm)
- Weight (kg)
- BMI (kg/m^2), to be calculated as: $\text{BMI} = \text{Weight (kg)} / (\text{Height (m)})^2$

Categorical variables (using frequency counts and percentages):

- Age (18-<65, 65-<85, ≥ 85 years)
- Age (≤ 18 , 19-<65, ≥ 65 years)
- BMI ($< 30 \text{ kg}/\text{m}^2$, $\geq 30 \text{ kg}/\text{m}^2$)
- Weight ($< 50\text{kg}$, $50\text{kg}-<70 \text{ kg}$, $70-<100\text{kg}$, $\geq 100\text{kg}$)
- Weight ($< 50\text{kg}$, $\geq 50\text{kg}$)
- Weight ($< 70\text{kg}$, $\geq 70\text{kg}$)
- Sex (Male, Female)
- Race (American Indian or Alaskan native, Asian, Black, Native Hawaiian or Other Pacific Islander, White, Other/Mixed)
- Ethnicity (Hispanic or Latino, Not Hispanic or Latino)
- Region (North America, Europe, Asia [excluding Japan], Japan)
- Country
- Needed rescue therapies in the observation period of MG0003 and entered MG0004

Note: Height captured at screening visit from MG0003 CRF will be summarized and used in BMI calculation. Other variables listed here are captured from MG0004 CRF.

A by-participant listings of demographics will be provided using the RS. Childbearing potential and lifestyle will be listed using the ES separately.

6.2 Other Baseline characteristics

The following variables will be summarized by treatment group and RLZ total for the RS. The baseline values are derived according to [Section 3.3](#).

- Baseline MuSK antibody status (positive, negative)
- Baseline AChR antibody status (positive, negative)
- Baseline MG-ADL score
- Baseline MG-ADL category (< 5 , ≥ 5)
- Baseline QMG score
- Baseline MG-C score
- Baseline total IgG value

6.3 Medical history and concomitant diseases

Any medical conditions that were not reported in MG0003 will be captured on CRF of this study and listed using the RS. Besides, procedure history will be provided in separate by-participant listings using the RS.

6.4 Prior and concomitant medications

The number and percentage of participants taking Prior or Concomitant medications will be summarized using the RS by Anatomical Therapeutic Chemical (ATC) class, presenting as Anatomical Main Group (ATC Level 1), Pharmacological Subgroup (ATC level 3), Preferred Term (PT), treatment group and RLZ total. The number and percentage of participants taking steroids, Immunosuppressants and AChE Inhibitors will be summarized.

Additionally, rescue medications are those that are mentioned in Protocol section 6.5.3 and identified:

- if Rescue Medication is ticked as yes on CRF Concomitant Medication page
- Or PEX as procedure entered on CRF Concomitant Medical Procedure page

The start date of rescue medication should be on or after Baseline. All rescue medications will be summarized using the RS.

Medications classified as prior or concomitant will be listed using the RS. A by-participant listing of participants taking steroids, immunosuppressants and AChE Inhibitors will be listed, including ADD at Baseline, ADD at last study visit and change from Baseline in ADD (See [Section 11.1](#)). A by-participant listing of concomitant procedures will also be listed using the RS. Originally reported dates will be used for listings.

6.4.1 Categories of prior and concomitant medications

Medications will be classified as follow based on imputed start and stop dates & times as outlined in [Section 4.2.2](#).

- **Prior** medications will include any medications that started before the first administration of IMP in MG0004.
- **Concomitant** medications will include any medications that have been taken at least once after the first administration of IMP during the Treatment and/or Observation Period of MG0004.

Medication Started	Medication finished	Classification
Before 1st Dose IMP	Any time	Prior
Any time	After 1st Dose IMP	Concomitant

6.4.2 Assignment of medications to study period

The following rules will be used to assign a concomitant medication to a study period:

- **Treatment Period:** a medication will be assigned to the Treatment Period if it has been taken at least once between the first administration of IMP on Day 1 and 7 days after the last dose of IMP.
- **Observation Period:** a medication will be assigned to the Observation Period if it has been taken at least once from the day after Treatment Period to the EOS visit.

Thus, a medication taken from the time of the first drug administration in the Treatment Period to the end of the study will be assigned to the Treatment Period and the Observation Period.

7 MEASUREMENTS OF TREATMENT COMPLIANCE

Not applicable. The summaries of infusions will be detailed in [Section 8.1](#).

8 SAFETY ANALYSES

All safety analyses will be presented using the SS. Listings will be presented by treatment group and participant; tabulations will be presented by treatment group. Unless otherwise specified, safety analyses will be presented by the most recent dose the study participants received in MG0004 as described in [Section 3.6](#).

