The aim of MG0004 is to compare safety (primarily) of long-term treatment of 2 dose levels of rozanolixizumab. Rescue medication is allowed and is expected to be temporary; dose switching (up or down) is also allowed. Using a treatment policy estimand is considered the only viable option to deal with this complexity. Indeed, a hypothetical estimand that appropriately accounted for treatment switching in this study, differing lengths of treatment in MG0004, and differing exposure to rescue medications in both studies would be very assumption-rich. This estimand will be based on the Safety Set (SS).

For all variables, the population is the study participants meeting the protocol-specified inclusion/exclusion criteria. The main intercurrent events are the use of rescue medication during the course of the study, withdrawal due to TEAEs and treatment switching.

All safety variables, biomarkers, and anti-drug antibody (ADA) results will be summarized for the SS classified by first treatment dose received [REDACTED] in this study (ie, before any switching occurs), both with and without subdivision by treatment dose received in MG0003 (placebo or [REDACTED]).

Efficacy variables will be summarized using a ‘treatment policy’ approach as follows:

- Participant-level outcome: The given variable and time point being summarized (eg, value of MG-ADL at Week 5).
- Population-level summary measure: For categorical variables, unadjusted proportions by first treatment received and, for continuous variables, unadjusted means by first treatment received.

Missing values will not be imputed.

Further details will be provided in the Statistical Analysis Plan (SAP).

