9.1 Definition of analysis sets

The following analysis sets will be created in the study:

- Enrolled Set: All study participants who sign the informed consent.
- Randomized Set: All enrolled study participants who are randomized.
- Safety Set: All randomized study participants who received at least 1 dose of study medication in this study. Analysis of this set will be according to the treatment the study participants first received, and will be used for the efficacy, demographic, and safety analyses.

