9.2 General statistical considerations

Statistical evaluation will be performed by the Sponsor or designee and supervised by the Exploratory Statistics Department of UCB. Data will be summarized by dose levels of rozanolixizumab first received in this study.

All analyses will be performed using SAS[®] version 9.3 or later (SAS Institute, Cary, NC, USA). Continuous variables will be summarized by visit (where applicable) with the statistics including the number of study participants, mean, standard deviation (SD), median, minimum, and maximum. Categorical variables will be summarized by visit (where applicable) using frequency counts and percentages.

If not otherwise stated, Baseline values will be the last available predose value and will be clearly defined in the SAP. All relevant data will be listed by treatment group and study participant.

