8.2.2 Adverse events summaries

TEAEs will be summarized by the most recent dose level prior to onset of TEAEs and RLZ total, including the number and percentage of study participants and frequency. Additional details are described below:

1. Overview of TEAEs will include following categories: any TEAEs, serious TEAEs, participant discontinuation due to TEAEs, permanent withdrawal of IMP due to TEAEs,

temporary withdrawal of IMP due to TEAEs, TEAEs requiring dose change, treatment-related TEAEs, severe TEAEs, TEAEs leading to death, all deaths (AEs leading to death).

2. Incidence of TEAEs will be summarized by SOC, HLT, PT for:

- Any TEAEs
- Any TEAEs during Treatment Period
- Any TEAEs by maximum intensity (mild, moderate and severe)
- Any TEAEs by relationship
- Severe TEAEs
- Non-serious TEAEs above reporting threshold of 5% of study participants
- Fatal TEAEs
- Fatal TEAEs by relationship
- Serious TEAEs
- Serious TEAEs by relationship
- Participant discontinuation due to TEAEs
- TEAEs leading to permanent withdrawal of IMP
- TEAEs leading to temporary withdrawal of IMP
- TEAEs requiring dose change
- Treatment-emergent AESM
- Treatment-emergent AESI

3. Incidence of any TEAEs will be summarized by decreasing frequency of PT.

AESMs include severe headache, severe GI disorders (i.e., abdominal pain, diarrhea, vomiting), and opportunistic infection.

AESIs are the cases of potential Hy's Law (see [Section 8.3.1](#)).

AESMs and AESIs will be identified based on the assessment by the Investigator as recorded in the CRF. An AE will be counted as an AESM if there is a 'yes' response to the question "Adverse event of Special Monitoring?" and 'no' otherwise. An AE will be counted as an AESI if there is a 'yes' response to the question "Adverse Event of Special Interest?" and 'no' otherwise.

When applicable adverse event summaries will be ordered by alphabetical SOC, alphabetical HLT within SOC and decreasing frequency of PT in the RLZ total column for tables.

Listings of all TEAEs, all non-serious TEAEs, serious TEAEs, permanent withdrawal of IMP due to AEs, study participant discontinuation from study due to AEs, AEs leading to death, AESIs, AESMs will be presented by treatment group and participant. Persistent AEs and TEAE will be flagged in the listings. Most recent dose will be presented in listing even when the AE start date is partial.

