8.2.3 Adverse events of focus

Rozanolixizumab adverse events of focus (AEOF) include the following categories:

- Headaches
- Gastrointestinal disturbances
- Hypersensitivity reactions
- Anaphylactic reactions
- Injection site reaction
- Infusion reaction
- Infections
- Opportunistic infections
- Reductions in albumin and plasma proteins
- Effects on the kidney
- Drug related hepatic disorders
- Effects on lipids

1. The number and percentage of study participants who experience each category of the AEOF will be summarized by most recent dose level prior to onset of the AEOF and RLZ total treatment group. The following summaries will be presented by SOC, HLT, and PT:

- AEOF
- Serious AEOF
- AEOF by relationship
- AEOF by maximum intensity (mild, moderate and severe)

2. Additionally, the summaries for the AEOF headache and gastrointestinal disturbances in Treatment Period by intensity will be presented separately by most recent dose level and RLZ total.

3. Graphs for AEOF headache in Treatment Period by time of onset (relative to infusion), severity, causality and duration for each study participant will also be provided.

A by-subject listing of all AEOF by category (as listed above) will be provided by treatment group and participant. Most recent dose will be presented in listing even when the AE start date is partial. Further details related to the statistical analysis of the above mentioned treatment-emergent AEOFs are provided in [Section 13.8](#).

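### The SAP groups both primary safety endpoints by most recent dose, not by first dose received as the protocol requires, and does not record the change

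*SAP*

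**What the plan says.** **Protocol.** The estimand text in Section 3 gives the purpose: "The aim of MG0004 is to compare safety (primarily) of long-term treatment of 2 dose levels of rozanolixizumab". It adopts a treatment-policy strategy, names treatment switching as an intercurrent event, and sets the grouping: "All safety variables, biomarkers, and anti-drug antibody (ADA) results will be summarized for the SS classified by first treatment dose received". This is to be done "both with and without subdivision by treatment dose received in MG0003". Section 9.1 repeats the rule for the Safety Set ("Analysis of this set will be according to the treatment the study participants first received") and Section 9.2 applies it generally ("Data will be summarized by dose levels of rozanolixizumab first received in this study").

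**SAP.** Section 8 sets a different default: unless otherwise specified, "safety analyses will be presented by the most recent dose the study participants received in MG0004". Section 8.2.2 confirms it for adverse events: "TEAEs will be summarized by the most recent dose level prior to onset of TEAEs and RLZ total". The tables under that rule include any TEAE and TEAEs leading to permanent withdrawal of IMP, which are the two primary endpoints in SAP 2.2.1.1. Adverse events of focus (8.2.3) are likewise "summarized by most recent dose level prior to onset of the AEOF and RLZ total treatment group", and the Japan TEAE tables (11.2) follow the same pattern. SAP 3.6 defines both groupings, and first dose remains the default for efficacy (Section 9) and for exposure duration (8.1).

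SAP 1 states that changes from the protocol analyses are documented in 3.9.

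**The concern.** First-dose groups are essentially the randomised groups, and comparing them is what a treatment-policy estimand asks for. A dose group that changes within a participant is something else. Protocol 4.2 and 6.6 allow a switch at the Investigator's discretion, in one direction after TEAEs and in the other after symptom worsening. Who contributes time to each column therefore depends on events after randomisation.

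An event stays with the dose taken at its onset. Only events starting after a switch move to the new dose. If participants prone to adverse events leave one dose, that column loses some of their later events and the other gains them.

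There is also a denominator problem. A switcher can belong to both columns, while a participant without an event has no onset date by which to be assigned to either. The general percentage rules in SAP 3.1 do not settle N for a time-varying column.

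**Working it through.** **1. Text comparison**

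| Item | Protocol | SAP |
|---|---|---|
| Safety grouping | First dose (3, 9.1, 9.2) | Most recent dose (8, 8.2.2) |
| Split by MG0003 treatment | Required for all safety variables (3) | Only some ADA tables (10.3.2) |
| Tables of either primary endpoint by first dose | Required | 0 |
| Tables of either primary endpoint by MG0003 treatment | Required | 0 |
| Grouping change recorded in SAP 3.9 | – | 0 of 4 entries |

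The four entries in 3.9 cover two dropped MG Symptoms PRO totals, a reworded concomitant-medication objective, replacement of the steroid AUC, and the sample size of 240 rather than 276. The other TEAE tables in the SAP (10.3.2) are by ADA category.

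**2. Possible size (illustrative)**

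The plan gives no figure to reproduce. The doses are redacted and every rate below is assumed. The endpoint is a TEAE leading to withdrawal. Assumptions:

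- 1 adverse event per year on the reference dose, times a rate ratio (RR) of 2 or 1 on the dose that participants leave because of TEAEs
- 20% of events lead to withdrawal
- exposure T uniform from 6 to 52 weeks (0.1154 to 1 year, width 0.8846)
- at most one switch
- with or without a participant-specific gamma frailty (shape 1, mean 1)

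*No-switch reference, RR 2.* The withdrawal-event rates are 0.2 and 0.4 per year.

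- Without frailty, P = 1 − [exp(−0.1154r) − exp(−r)] / (0.8846r). This gives 10.4% for r = 0.2 and 19.6% for r = 0.4, a gap of 9.1 points.
- With frailty, P = 1 − ln[(1+r)/(1+0.1154r)] / (0.8846r). This gives 9.85% and 17.66%, a gap of 7.8 points.

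*With switching.* Simulation of 400,000 per arm, Monte Carlo error about 0.1 point. Each cell is the gap in points (dose left for TEAEs minus the other dose), by first dose → by most recent dose, the latter divided by everyone who ever received that dose. Columns give the assumed probability that an adverse event prompts a switch. *Opposite* adds AE-independent switching the other way, assigned to 40% of the other arm, of whom enough remain on treatment that about 21% of the arm switches.

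| Scenario | 10% | 25% | 50% |
|---|---|---|---|
| RR 2, frailty, one-way | 7.4→6.5 | 6.3→4.5 | 5.6→2.5 |
| RR 2, frailty, opposite | 6.0→6.6 | 5.3→5.1 | 4.4→3.2 |
| RR 2, no frailty, one-way | 8.6→8.3 | 8.0→7.4 | 7.3→6.0 |
| RR 2, no frailty, opposite | 7.5→8.7 | 6.8→7.7 | 5.8→6.3 |
| RR 1, frailty, one-way | – | – | 0.0→−2.1 |
| RR 1, frailty, opposite | – | – | −0.1→−1.4 |
| RR 1, no frailty, one-way | – | – | 0.1→−0.6 |
| RR 1, no frailty, opposite | – | – | −0.2→−0.2 |

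The extreme shifts are 2.5 − 5.6 = −3.1 and 8.7 − 7.5 = +1.2 points.

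**3. Scale**

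The −3.1 case has first-dose levels of 9.9% and 15.4%. At 120 per arm (240 / 2), SE = √(0.099×0.901/120 + 0.154×0.846/120) = √(0.000743 + 0.001086) = 0.043, or 4.3 points.

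**4. Denominator**

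With RR 2, frailty, 25% AE-driven and 40% opposite switching, about 138 participants ever receive one dose and 145 the other. The sum is 283 for 240 people, so 283 − 240 = 43 are counted twice. By first dose the Ns are 120 and 120.

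**The case against.** **The objective is not comparative.** The stated primary objective is to evaluate long-term safety and tolerability. The rozanolixizumab total column does that and is unaffected by grouping, and all analyses are descriptive. This limits the harm. It does not remove the protocol's explicit aim of comparing two dose levels or its explicit grouping rule.

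**First dose is not the truth either.** It is itself diluted by switching. Without frailty and with opposite switching, the most-recent-dose gaps (8.7, 7.7, 6.3) lie closer to the no-switch gap of 9.1 than the first-dose gaps do (7.5, 6.8, 5.8). Also without frailty, events per person-year by most recent dose return the assumed 0.20 and 0.40, so the shift there comes from the ever-received denominator. Both points stand. The two groupings estimate different quantities, and the protocol chose the first-dose one. With frailty, a real selection effect remains.

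**Other tables partly cover the gap.** SAP 5.1 plans discontinuation due to AEs on the Randomized and Safety Sets, but it counts leaving the study, not TEAEs or withdrawal of study medication. SAP 8.1 shows the number of participants with a dose change by visit and lists all administrations, so switching is visible, but time on each dose is not summarised. The amendment log (14.1) says AE summaries were reorganised to match MG0003; that is SAP version history, not a record of departure from the protocol.

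**The illustration is thin.** Every rate is assumed, only the withdrawal endpoint is modelled, and the largest shift is below one standard error. This is correct, and the case rests on the text mismatch rather than on these figures.

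**Conclusion.** The concern holds. The SAP replaces the protocol's grouping for both primary safety endpoints, omits the required MG0003 split for them, and leaves the change out of the section meant to record it. This follows from the text and needs no assumption. The same departure reaches the laboratory, vital-sign and ECG tables (SAP 8.3, 8.4.1, 8.4.2), which also use most recent dose.

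The effect on the displayed dose contrast is uncertain in size and direction: about −3.1 to +1.2 points in the scenarios above. One-way AE-driven switching shrinks a real difference, and with frailty it can produce an apparent one where none exists. Switching the other way can leave the gap unchanged or widen it. Overall TEAE incidence is not affected. The point should be fixed before the tables are produced, but it does not threaten the study's total safety summary.

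**What to change.** - In SAP 3.6, 8 and 8.2.2, make first dose received the primary presentation for TEAEs and for TEAEs leading to permanent withdrawal of IMP, with and without subdivision by MG0003 treatment.
- Keep most recent dose at onset as a labelled supportive display. Define its N (for example, participants who ever received that dose) and report person-time on each dose beside it.
- Align the Safety Set wording in SAP 3.5.3 (treatment actually received) with protocol 9.1 (treatment first received). This is minor, since 3.5.3 already refers to 3.6.
- Record in SAP 3.9, with a reason, any departure that is kept, including most recent dose for laboratory, vital-sign and ECG tables.

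The cost is SAP wording and a repeat of existing TEAE tables with a grouping variable that SAP 3.6 already defines. The downside is more tables; no new data are needed. A justified entry in 3.9 alone would make the departure transparent, but would not supply the comparison the protocol specifies.
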